The recent development of novel ankle foot orthoses (AFO) have led to significant improvements in walking ability in patients, particularly those with impaired ambulation (e.g., patients with a stroke). The AFO (Figure 1) are made of light-weight, low profile carbon-fiber materials that store elastic energy early in a footstep followed by a release of the stored energy during the propulsive phase of walking that assists calf muscle function. These devices are relatively low cost and minimally invasive and may acutely improve PAD patients' ability to walk. To date, using an AFO to circumvent restrictions to walking (calf pain) in PAD have not been completed and may provide patients with an opportunity to improve their walking ability. Additionally, the impact of an AFO on biomechanical parameters in PAD patients is unclear as there are few studies examining this important component of ambulation. A full assessment of calf muscle function using motion analysis may provide new insight into the mechanistic limitations PAD patients' experience. Thus, an AFO used to aid PAD patients' walking ability could potentially lead to a new therapeutic method for PAD patients.

A.2. Hypothesis and specific aims

We will test the hypotheses that PAD patients using an AFO during a graded exercise test will demonstrate a greater peak walking time (PWT) compared to PWT assessed without the use of the AFO.

Specific Aim 1. Examine the effect of an AFO on the primary outcome of PWT assessed using a graded treadmill test for PAD patients. Determination of PWT (defined as the maximal time a patient walks on a graded treadmill test) with and without the AFO will be important for understanding its potential utility for improving walking ability in PAD. Secondary outcomes will include claudication onset time (COT), defined as the point when leg pain first occurs during walking, functional ability (assessed via the 6-minute walk test) and peak oxygen consumption (VO_{2peak}) with and without the AFO.

Specific Aim 2. Evaluate the capacity of an AFO to assist calf muscle function during walking in patients with PAD and IC. The device may decrease the mechanical demands of the calf, thus patients will receive a motion analysis assessment during walking with and without the AFO. Outcomes will include ankle power during propulsion and calf muscle recruitment analyses using electromyography sensors during walking.

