Specific Aim 3. Examine the effects of an AFO following a walking exercise program. The device may improve primary and secondary outcomes following 12 weeks of community walking (standard of care). Outcomes will include PWT, COT, functional ability, VO_{2peak} and patient-reported outcomes assessed with the Walking Impairment Questionnaire (WIQ) and the Medical Outcomes Study Short Form 36-item questionnaire (SF-36).

B. Study Design and power calculation

B.1. Study design

The proposal will utilize a prospective cohort design. We will recruit a total of 15 male and female patients with PAD and IC who are ≥40 years of age. Patients will be diagnosed with PAD at the vascular clinics of the International Heart Institute (IHI) within St. Patrick Hospital and its affiliated outreach sites within their network of providers or will be screened per standard guidelines if not receiving care from IHI (see **D.2.d. Ankle-brachial index assessment**).

B.2. Power calculation

Sample size was calculated to evaluate differences in PWT with the AFO vs. without during graded exercise testing. The estimates were based on data from a previously conducted clinical trial¹⁴ composed of 25 PAD patients who were randomized to a new detailed community-based walking program or the standard of care (upfront advice to exercise). Based on an effect size of 0.94, a sample of 12 patients is estimated to provide 80% power at α =0.05 to detect a significant difference in PWT. To account for a 20% attrition rate, 3 additional patients are needed (total sample n=15).

C. Patient recruitment and inclusion/exclusion criteria

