- **D.2.e.** Graded exercise tests: The graded exercise tests will be conducted on a treadmill using the Gardner protocol as previously described¹⁷ with continuous electrocardiogram monitoring in the Montana Peripheral Artery and Cardiac Exercise (PACE) Laboratory (directed by [name]) at IHI. Patients will complete two separate outcome assessment visits within 1 week. Outcomes will be assessed with the AFO and without the AFO over the first 2 baseline visits (order randomized to avoid test bias). PWT (min) will be recorded as the maximal time the patient can walk on the treadmill before having to stop due to severe leg pain (Specific Aim 1). COT (min) will be obtained with the patient pointing to the pain scale at the initial presentation of leg pain. An open-circuit respiratory-metabolic system will be used to measure VO_{2peak} (ml·kg⁻¹·min⁻¹).
- **D.2.f. Functional ability and patient-reported outcomes:** Patients will complete the 6-minute walk test with and without the AFO during the two separate outcome assessment visits to evaluate the immediate effect of the AFO. Patients will walk in a 50 foot corridor at the hospital as previously reported. Maximal walking distance achieved in 6-minutes and COT will be assessed at each outcome time point. The WIQ and SF-36 questionnaires will be administered as previously described. Page 19,20
- **D.2.g.** Three-dimensional gait analysis of self-paced walk: Motion analysis testing for lower extremity joint kinetics (forces) and kinematics (motion) during self-paced walking will be performed using an eight-camera motion analysis system with two force plates (**Specific Aim 2**). Anatomical landmarks for the trunk, pelvis, thigh, and shank (part of the leg between the knee and ankle) will be placed per [name] published methods involving gait analysis of

patients with total knee arthroplasty.^{21,22} Recruitment levels for the calf during propulsion will be measured via surface electromyography sensors and analyzed using established methods.²³ Multiple trials of walking with and without the AFO will be compiled for analysis (~1 hour). The outcomes to be measured are ankle power during propulsion and calf muscle recruitment.

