- Graded exercise test and exercise training: Graded exercise tests are standard procedure conducted in hospital settings (thousands of advanced cardiovascular patients every year receive these tests). The cardiac event rate in a mixed adult population (includes acute myocardial infarction, ventricular fibrillation, hospitalization and death) is approximately 6 per 10,000 tests. ²⁴ Other minor risks of the graded exercise test include dryness of the mouth/throat or slight bleeding of the gums due to the respiratory-metabolic analyzer mouthpiece. The risks associated with the standard of care for walking exercise and PAD are minimal as virtually healthcare providers encourage patients to adopt a walking exercise program.
- AFO: There is a small risk of discomfort and skin wear from the AFO where it contacts the lateral and/or medial part of the ankle. The strapping that holds the shin plate in place can also apply some pressure leading to potential discomfort and areas of wear on the skin. Additionally, there may be a risk of falling while using the devices.
- Motion analysis: The only risk associated with the motion analysis tests is minor skin irritation or discomfort when removing the adhesive tape that is used to hold reflectors and sensors to the skin.

G. Measures to minimize potential risks and discomforts

- Confidentiality and privacy: Personal identifying information will not be included, when possible, and study visits will be conducted in a private setting. Potential embarrassment during community-based exercise will be minimized, as patients can choose where they exercise (e.g., park, neighborhood) in addition to the AFO being a low-profile device (unlike walking canes or strollers).
- Blood draw: Standard methods for extracting blood samples for subsequent analysis will be followed. Samples will be obtained from trained phlebotomists at St. Patrick Hospital.
- ABI: To ensure appropriate assessment of patient's arm and ankle pressures, standard procedures will be conducted per published methods. We will not inflate the cuff above 220 mmHg and the rate of pressure decrease will be in accordance with best practices.

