- Graded exercise test: [name] (PI) has extensive experience in clinical exercise testing and training for patients with PAD. The IHI has a full complement of Advanced Cardiovascular Life Support (ACLS) certified healthcare providers (e.g., cardiologists, physician assistants, nurse practitioners) to monitor exercise stress test electrocardiograms for patients enrolled into the trial. [name] is the study doctor for this trial and will provide oversight of stress testing. IHI has necessary resuscitative equipment (e.g. crash carts) and trained personnel available if a patient experiences an adverse event during exercise testing. Additionally, in the event of an acute myocardial infarction during exercise testing, the IHI Cardiac Catheterization laboratory is ~50 meters from the Montana PACE lab. The stress tests are critically important for determining the safety of any exercise activity the patients will complete. The likelihood of an adverse event caused by exercise training is most likely to occur during the stress test when the critical equipment and personnel are available to respond to such an event. Patients who are unable to safely complete the graded exercise test due to an abnormal event will be categorized as high risk and excluded from participation in the trial. The dryness of the mouth and throat will be minimized by allowing the patient to drink water prior to the test as needed. A thorough description of the device will be explained to patients' (informed the mouthpiece is similar to "snorkel" or "mouth guard") and that slight bleeding of the gums from contact with the mouthpiece is not serious and common during use.
- Vulnerable populations: Pregnant woman may not be included in this study. Pregnancy testing will be requested if their menstrual cycle is more than one week overdue or if they suspect they are pregnant. We don't anticipate this

- being a concern, as the average age of PAD patients is in the mid-60's and thus the vast majority of women PAD patients are post-menopausal.

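### Do the two wordings of peak walking time, and the section G exclusion rule, leave the primary endpoint open in a way that matters?

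*Combined protocol and SAP*

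**What the plan says.** Section A.2 names PWT as the primary outcome and gives its meaning under Specific Aim 1: "PWT (defined as the maximal time a patient walks on a graded treadmill test". No reason for stopping is attached.

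Section D.2.e describes how PWT is recorded: the "maximal time the patient can walk on the treadmill before having to stop due to severe leg pain". It labels this measure as belonging to Specific Aim 1. The treadmill method is given by citation, and the text lists no stopping criteria.

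The Aim 1 comparison is within patient: "Outcomes will be assessed with the AFO and without the AFO over the first 2 baseline visits (order randomized to avoid test bias". Table 2 places these two tests at Visits 2 and 3, before the 12 weeks of community walking.

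Section G adds a safety rule: patients "unable to safely complete the graded exercise test due to an abnormal event will be categorized as high risk and excluded from participation". It says nothing about walking times already recorded. The document has no separate analysis section, analysis set or missing-data rule.

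**The concern.** A primary endpoint should have one definition. Under Aim 1, a test that ends through breathlessness, fatigue or device discomfort yields a PWT. Under D.2.e taken literally, it does not.

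The difference could fall unevenly on the two conditions. Section A.2 says of the orthosis: "The device may decrease the mechanical demands of the calf". If that is so, leg pain may end fewer tests with the device than without it. Section F gives a reason for device-related stops: "There is a small risk of discomfort and skin wear from the AFO". If times from non-pain stops were set aside, pairs could be lost for reasons linked to the treatment effect. The patients lost might be those the device helped most, because they had walked past their usual pain limit.

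The section G rule raises a second question. If a patient is excluded after the second baseline test, two times exist and the plan does not say whether the pair counts. With at most 15 pairs, each one is visible in the result.

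**Working it through.** **1. The two wordings compared**

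| How the test ends | Aim 1 (A.2) | D.2.e, read literally |
|---|---|---|
| Severe leg pain | time walked | time walked (same value) |
| Other reason, no safety event | time walked | not stated |
| Abnormal event (section G) | time walked, patient excluded | not stated, patient excluded |

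The first row is the expected ending in patients enrolled for claudication. Section C.1 excludes patients limited mainly by lung disease, angina or heart failure, although a physician may override an exclusion. For the second row, no sentence directs that the time be discarded, and Aim 1 supplies the value.

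**2. The plan's own sample size**

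Inputs from B.2: effect size 0.94, α = 0.05, 80% power, 12 evaluable patients, 20% attrition. B.2 gives neither the type of effect size nor the sidedness. I assume a standardised paired difference and a two-sided paired t-test (noncentral t with n − 1 degrees of freedom and noncentrality 0.94 × √n).

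- The smallest n reaching 80% is 11 (80.2%). At n = 12 power is 84.2%, close to the stated "a sample of 12 patients is estimated to provide 80% power".
- Attrition: 12 / (1 − 0.20) = 15, as stated.
- A two-group reading would need 18 per arm, which does not match 12, so the paired reading fits better.

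**3. Power if pairs are lost (same assumptions)**

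| Pairs | 15 | 14 | 13 | 12 | 11 | 10 |
|---|---|---|---|---|---|---|
| Power | 92.2% | 90.1% | 87.5% | 84.2% | 80.2% | 75.4% |

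The Aim 1 pair is complete by Visit 3, so dropout during the 12-week phase does not reduce it. Up to 15 pairs may be available, and four can be lost before power falls below 80%.

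**4. How often the section G question can arise**

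An event in the first baseline test leaves no pair, so there is nothing to decide. Only the second test matters, which is 15 tests. Section F says the cardiac event rate "is approximately 6 per 10,000 tests", or 0.0006 per test.

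- Expected events: 15 × 0.0006 = 0.009.
- Chance of at least one: 1 − (1 − 0.0006)^15 = 0.9%.
- An abnormal event may be a broader class. If its rate were ten times higher (assumed, 0.006): 15 × 0.006 = 0.09 expected, and 1 − (1 − 0.006)^15 = 8.6%.

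**5. What one pair could do to the estimate**

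If one pair of 15 lies D standard deviations from the mean of the other 14, leaving it out moves the mean by D/15. The standard error with 15 pairs is 1/√15 = 0.258 SD. D is assumed; the documents give nothing on it.

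| D (assumed) | Shift (SD) | Share of standard error |
|---|---|---|
| 0.5 | 0.033 | 13% |
| 1 | 0.067 | 26% |
| 2 | 0.133 | 52% |

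For section G events at the stated rate and D = 1, the expected shift is 0.009 × 0.067 = 0.0006 SD. No rate is given for other non-pain stops, so their effect cannot be sized.

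**The case for a change.** The strongest case for a change is that stop reasons may depend on the condition being tested. A device that relieves the calf may let patients walk until something other than leg pain stops them, and a literal D.2.e rule would lose those times more often with the device. The physician override in C.1 also lets in patients with other exercise limits. The remedy would be cheap: matching sentences, a stop-reason field and one table.

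The difference in wording and the silence on recorded pairs do stand, and differential stopping is plausible. What is missing is a step from there to a wrong analysis. Harm would require someone to discard observed walking times on a rule the plan does not contain and against the Aim 1 definition. Section G also describes fitting by a specialist, cushioning and practice with the device, which reduces discomfort-related stops. Its exclusion rule reads naturally as a safety screen for exercise. A stop-reason table would be informative, but no result in the plan depends on it.

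**Conclusion.** No change follows. D.2.e is best read as a practical description, for a claudication population, of the quantity Aim 1 defines. The remaining gap is one that analysts fill sensibly by using the time walked. The section G question is confined to an event in the second baseline test, with about a 0.9% chance across 15 patients at the protocol's cardiac event rate, or about 9% if abnormal events were ten times as common. Losing one pair would leave power near 90%, and losing four would leave it at 80%.

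The power figures rest on reading 0.94 as a paired standardised difference in a two-sided test. The shift figures rest on an assumed departure for the omitted pair. The frequency of other non-pain stops is unknown, so a small effect in either direction cannot be ruled out, but none has been shown.
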